12.2.7.5 Exploratory Efficacy Endpoints

Analysis of exploratory efficacy endpoints will not be subject to Type I error control. Statistical tests will be 2-sided with a nominal type I error rate of 0.05.

EORTC-QLQ-C30-QoL: As per the user's manual, raw scores for the EORTC-QLQ-C30 will be transformed using a linear transformation to standardize the results so that scores range from 0 to 100. At each assessment point, summary statistics of absolute scores and changes from baseline will be calculated by treatment group for each scale for both the raw score and the linear transformed score. Scores will be compared between treatments over time using mixed model repeated measures.

EQ-5D: The EQ-5D data will be scored and handled as recommended in its user's manual, and analyzed in a similar way to the EORTC-QLQ-C30.

FACT-B: The FACT-B data will be scored and handled as recommended in its user's manual, including handling of missing data both within the subscales and overall. The scores will be summarized by randomized treatment group at each assessment point. The scores will also be analyzed over time using mixed model repeated measures analysis in a similar way to the EORTC-QLQ-C30 and EQ-5D.

The analysis of the EORTC-QLQ-C30, EQ-5D and FACT-B will be performed in the PRO Population.

Relationship between biomarkers and clinical outcome: The relationship between baseline biomarkers (including ER status, PgR status, CXCR4 expression levels, cytokines [e.g. IFN-gamma], immune cells profile and RNA expression) and ORR, PFS and OS will be explored using a variety of exploratory data analysis methods including Cox and logistic regression models, time dependent covariate analysis (for biomarker measured longitudinally) and multivariate stepwise model selection methods. All such analyses will be essentially descriptive and hypothesis generating in nature.

12.3 3rd line + Population Efficacy Analysis Plan relevant to the US and other jurisdictions in which the 3rd line + Eribulin Label applies

12.3.1 Sample Size

Assuming a median PFS on eribulin of 3.9 months, to test for a hazard ratio versus balixafortide + eribulin of 0.674 (corresponding to a median PFS of 5.8 months), a total of 286 PFS events are required to provide 90% power at the 1-sided 2.0% alpha level. Assuming a 12-month, non-linear recruitment period (η =2; Carroll, 2009(3)) and a minimum 12-month follow-up period after the last patient is randomized, a total of 320 3rd line + patients will be recruited.

12.3.2 Analyses Sets

12.3.2.1 3rd line + Population

The following analysis sets are defined for the 3rd line + population:

• **ITT Population (3rd line +)** is defined as all randomized patients in the 3rd line + population. Efficacy data in this population will be summarized by randomized

Protocol No.: POL6326-009

Version 3.0

treatment. The co-primary endpoint PFS and key secondary efficacy endpoint OS will use the ITT population. Patients will be analyzed by the treatment arm to which they are randomized.

- Response Evaluable Population (3rd line +) will be used to evaluate disease response. The Response Evaluable Population includes all patients in the 3rd line + population who are randomized in the study with measurable disease by RECIST v1.1 (as determined by the Investigator). The co-primary endpoint analysis of ORR and other secondary endpoint analyses of CBR and duration of response will be conducted using the Response Evaluable Population. Patients will be analyzed by the treatment arm to which they are randomized.
- **PRO Population (3rd line +)** is defined as all patients in the 3rd line + population where the patient has at least one post randomization PRO value. Patients will be analyzed by the treatment arm to which they are randomized.
- **Safety Population** is the same as that defined for the overall, 2nd line + population.

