4.4 Endpoints

4.4.1 Overall Population Efficacy Endpoints

Primary Efficacy Endpoint

In the Overall Population intended for regulatory submissions in the EU and jurisdictions in which the 2nd line + eribulin label applies, the primary endpoint is:

Date: 15 July 2019

Protocol No.: POL6326-009

Version 3.0

PFS according to RECIST v1.1 guidelines, as assessed by the IRC.

Key Secondary Efficacy Endpoint

OS.

The statistical design in the overall, 2nd line+ population, with pre-defined alpha allocation and recycling, is such that if PFS does not meet statistical significance at its allocated alpha level, then the design still allows OS to be tested and, if it meets statistical significance at its allocated alpha level, then the study can still be formally positive for efficacy.

Other Secondary Efficacy Endpoints

- PFS according to RECIST v1.1 guidelines, as assessed by the local Investigator's review.
- ORR [confirmed CR + confirmed PR]) according to RECIST v1.1 guidelines, as assessed by the IRC in the Overall Population.
- ORR (confirmed CR + confirmed PR) according to RECIST v1.1 guidelines, as assessed by the local Investigator's review.
- CBR (proportion of patients with confirmed CR, confirmed PR, or SD ≥6 months) according to RECIST v1.1 guidelines as assessed by the IRC and by the local Investigator's review.
- Disease control rate (DCR; number of patients with confirmed CR, confirmed PR, or SD) according to RECIST v1.1 guidelines as assessed by the IRC and by the local Investigator's review.
- Time to response as assessed by the IRC and by the local Investigator's review.
- Duration of response as assessed by the IRC and by the local Investigator's review.

4.4.2 3rd Line + Population Efficacy Endpoints

Co-Primary Endpoints

In the 3rd line + population intended for regulatory submissions in the US and jurisdictions on which the 3rd line + eribulin label applies, the co-primary endpoints are:

- ORR (confirmed CR + confirmed PR) according to RECIST v1.1 guidelines, as assessed by the IRC.
- PFS according to RECIST v1.1 guidelines, as assessed by the IRC.

If PFS in the 3rd line + population is met at the allocated alpha level, PFS in the Overall Population will also be formally tested at the same alpha level.

Key Secondary Efficacy Endpoint

OS.

Protocol No.: POL6326-009

Version 3.0

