5. STUDY POPULATION

5.1 Patient Inclusion Criteria

Patients with measurable and non-measurable disease will be eligible for inclusion in this study only if all the following criteria are met:

- 1. Patients at least 18 years of age (or according to local regulation).
- 2. Documented histologically confirmed BC.
- 3. Metastatic BC currently of stage IV disease by American Joint Committee on Cancer criteria or unresectable locoregionally recurrent BC.
- 4. Molecular status and prior therapies:
 - a) Molecular Status
 - Eligible patients are, by their patient records and prior therapy, HER2 negative with any ER or PgR status. If a previous record of the HR status is not available, the HR status should be tested locally.
 - HER2 negative (IHC 0,1 or fluorescence in situ hybridization [FISH] or chromogenic in situ hybridization [CISH] HER2:CEP17 ratio < 2.0); HER2 2+ patients should be FISH/CISH negative.
 - b) Prior Therapies
 - Patients with locally recurrent or metastatic BC who have previously received 1–4 chemotherapeutic regimens for the treatment of locally recurrent or metastatic BC. Unless contra-indicated for safety reasons, prior therapy will have included an anthracycline and a taxane in either the adjuvant or metastatic setting.
 - Patients with HR positive status (ER+ and/or PgR+) must have been treated with at least one line of endocrine therapy and considered by the treating physician not to be a candidate for further endocrine therapy.
- 5. At least 14 days from the completion of any previous cytotoxic chemotherapy, biological therapy, or any other investigational agent at time of initiation of study medication. Resolution of chemotherapy and radiation therapy related toxicities to Grade 1 or lower severity, except for stable sensory neuropathy Grade 2 or lower and alopecia.
- 6. Patients must have proved refractory to the most recent chemotherapy, documented by progression on or within six (6) months of therapy.

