12.2.7.4 Other Secondary Endpoints

Analysis of the other secondary endpoints in the overall, 2nd line + population, i.e. ORR, CBR, DCR, time to response, and duration of response will not be subject to Type I error control. Statistical tests will be 2-sided with a nominal Type I error rate of 0.05.

ORR will be analyzed by exact logistic regression and be stratified for randomization stratification factors. The odds ratio will be estimated from the model along with the associated 95% CI and 2-sided p-value. Exact Clopper-Pearson 2-sided 95% CI limits will be calculated for the proportion of patients with ORR in each arm.

ORR analyses will be performed for the Response Evaluable Population. Patients who do not have measurable disease at baseline will be excluded from the population. In addition to presenting ORR, the best response using response categories CR, PR, SD, PD, and not evaluable (NE) will be tabulated. The proportion of the response in each response category will be calculated. Patients who do not have any post-baseline tumor assessment will be counted under the category NE. SD requires at least one post-baseline scan performed at 6 weeks (42 days) or later. Patients who did not have any post baseline scans for the 6 week assessment or later, and who also do not have a documented PD will be counted as NE.

Duration of response will be analyzed in the Response Evaluable Population, and CBR will be analyzed in both the Response Evaluable Population and ITT population.

CBR will be compared between the treatment arms using exact logistic regression as described for ORR. Exact Clopper Pearson 2-sided 95% confidence limits will be calculated for the CBR of each treatment arm.

Duration of response will be analyzed via Cox regression modelling with a fixed effect term for randomized treatment. The hazard ratio will be estimated from the model along with the associated 95% CI and 2-sided p-value. The data will also be displayed using Kaplan-Meier curves; median duration of response and the 95% CIs will be estimated from the Kaplan-Meier

Protocol No.: POL6326-009

Version 3.0

by treatment arm. A supportive analysis will be performed based on the expected duration of response as per Ellis et al (2008) (59).

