3.2.1. Co-Primary Efficacy Endpoint

In the 3rd line+ population intended for regulatory submissions in the US and jurisdictions on which the 3rd line+ eribulin label applies, the co-primary endpoints are:

- ORR (confirmed CR + confirmed PR) according to RECIST v1.1 guidelines, as assessed by the IRC.
- PFS according to RECIST v1.1 guidelines, as assessed by the IRC.

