4.3.6. Response Evaluable Set (3rd Line+)

The Response Evaluable (RE) set (3rd line+) will be used to evaluate disease response. The RE set (3rd line+) includes all randomized patients in the 3rd line+ population with measurable disease by RECIST v1.1 as determined by the Investigator at screening during the evaluation of breast cancer history. The co-primary endpoint analysis of ORR and other secondary endpoint analyses of CBR, duration of response, DCR and time of response will be conducted using the RE (3rd line+) set. Patients will be analyzed by the treatment arm to which they are randomized.

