The number of patients experiencing events and the number of censored patients will be summarized by randomized treatment arm with reasons for an event/censoring. The median survival times will be estimated by the Kaplan-Meier method and presented along with their corresponding 95% CI. The 25th percentile and 75th percentile for the survival times along with the corresponding 95% CI for the percentiles will also be displayed, CI will be calculated using method of Brookmeyer and Crowley (1982). Additionally, PFS probabilities at fixed time points i.e. 3, 6, 9, 12, 15 months will be derived from the Kaplan-Meier estimates with 95% confidence intervals, CI will be calculated using the Greenwood formula. The time points will be displayed based on the data availability.

Corresponding plots of Kaplan-Meier curves by treatment arm will also be presented. The plots will display the number of patients at risk every 3 months. Alongside this the PFS data will be presented in a listing by treatment arm.

Objective Response Rate

The ORR, defined from the best response as assessed by the IRC, will be analyzed by an exact logistic regression, stratified for randomization stratification factors excluding line of therapy (see Section 4.2 for further details). The odds ratio will be estimated from the model along with the associated 99.9% CI (0.001 alpha) and 2-sided p-value. Exact Clopper-Pearson 2-sided 95% confidence limits will be calculated for the proportion of patients with objective response in each arm.

ORR analyses will be performed for the RE (3rd line+) set and RE (3rd line+ Confirmed) set. Analysis of the RE (3rd line+ Confirmed) set is added as sensitivity and is not part of the alphacontrol for this study. In addition to presenting ORR, the best response as assessed by the IRC using response categories CR, PR, SD, PD and NE will be summarized. The number and percentage of patients in each response category will be presented by treatment arm. Patients who do not have any post-baseline tumor assessment will be counted under the category NE. SD requires at least one post-baseline scan performed at minimum of six (6) weeks (42 days) +/- seven (7) days, for a minimum time on-study of thirty-five (35) days or later. Patients who did not have any post baseline scans for the 6-week assessment or later and also do not have a documented PD will be counted as NE.

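### The co-primary ORR is read by the IRC but analysed in patients the investigator flagged as measurable, and no planned ORR analysis uses IRC-determined measurability

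*Protocol*

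**What the plan says.** - **Endpoint.** SAP 3.2.1 makes "ORR (confirmed CR + confirmed PR) according to RECIST v1.1 guidelines, as assessed by the IRC" a co-primary endpoint in the 3rd line+ population, as does protocol 4.4.2. The alpha is 0.001 2-sided (protocol 12.3.7.1, SAP 8.1.2).
- **Analysis set.** Protocol 12.3.2.1 builds the Response Evaluable set from randomized 3rd line+ patients "with measurable disease by RECIST v1.1 (as determined by the Investigator". SAP 4.3.6 adds when the flag is set: "as determined by the Investigator at screening during the evaluation of breast cancer history".
- **Who is enrolled and who is dropped.** Protocol 5.1 admits both kinds of patient: "Patients with measurable and non-measurable disease will be eligible for inclusion in this study". For ORR, protocol 12.2.7.4, which 12.3.7.1 applies to 3rd line+, says: "Patients who do not have measurable disease at baseline will be excluded from the population".
- **Response rules.** Protocol Table 5 defines PR by shrinkage of target lesions. For patients without measurable disease, Table 8 allows CR, Non-CR/Non-PD, PD or not evaluable. It has no PR row.
- **Sensitivity set.** The only other set for IRC ORR is Response Evaluable (3rd line+ confirmed), SAP 4.3.7. It is a subset of the main set and keeps the same flag.
- **Other analyses.** SAP 8.4 names the ITT (3rd line+) set for investigator ORR, but no ITT analysis of IRC ORR is planned.

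**The concern.** A response-evaluable set exists so that ORR is measured in patients who could show a response. Here one reader decides who can respond and another decides who did. Disagreement on baseline measurability can go two ways:

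- **Flagged, but no IRC target lesion.** The patient stays in the denominator and can count as a responder only through CR.
- **IRC target lesion, but no flag.** The patient is left out, even if the IRC later confirms a response.

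At stake are the size of the reported ORR and some power for a co-primary test that already runs at a strict alpha. As planned, the results would not show whether the ORR finding depends on the reader mismatch.

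**Working it through.** **Plan's own figure.** The documents give no power, assumed rates or expected reader disagreement for ORR, so there is no ORR figure to reproduce. The stated 3rd line+ PFS requirement does reproduce: 4 × (2.054 + 1.282)² / (ln 0.674)² ≈ 286 events. It has no bearing on ORR.

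**Inputs from the documents.** There are 320 3rd line+ patients randomized 1:1, so 160 per arm. Background ORRs, which are not design assumptions, are 9-12% for eribulin alone (protocol 2.2), and 30% (Phase 1 Overall Efficacy Population) and 38% (Expanded Cohort) for the combination (protocol 2.5.1).

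**Assumptions.**
- 130 flagged patients per arm (130/160 = 81%).
- f = share of flagged patients with no IRC target lesion: 5, 10 or 15%. CR in them is taken as nil.
- g = share of IRC-measurable patients without the flag: 0 or 10%, with the same ORR as the rest.
- Fisher's exact test at 2-sided 0.001, by full enumeration, stands in for the stratified exact logistic regression.

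**Reported ORR.** Reported ORR = true ORR × (1 − f). At f = 10%, 30% becomes 27.0% and 12% becomes 10.8%. The odds ratio moves only from 3.14 to 3.05.

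**Power.** The current set has 130 per arm, of whom 130 × (1 − f), rounded, can respond. The IRC-measurable set has that number when g = 0, and that number divided by 0.9 when g = 10%.

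| True ORR | f | Responsive n per arm | Power, current set | Power, IRC set, g = 0 | Loss (points) | IRC set n, g = 10% | Power, IRC set, g = 10% | Loss (points) |
|---|---|---|---|---|---|---|---|---|
| 30% vs 12% | 5% | 124 | 52.1% | 53.4% | 1.3 | 138 | 61.8% | 9.7 |
| 30% vs 12% | 10% | 117 | 47.0% | 49.0% | 2.0 | 130 | 56.5% | 9.5 |
| 30% vs 12% | 15% | 111 | 42.6% | 45.7% | 3.2 | 123 | 52.7% | 10.1 |
| 38% vs 12% | 5% | 124 | 92.0% | 92.6% | 0.6 | 138 | 95.8% | 3.8 |
| 38% vs 12% | 10% | 117 | 89.0% | 90.2% | 1.2 | 130 | 94.0% | 5.0 |
| 38% vs 12% | 15% | 111 | 85.8% | 87.8% | 2.0 | 123 | 92.2% | 6.4 |

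Losses are taken before rounding. At f = g = 0 the two sets coincide and the loss is zero.

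**Direction for the left-out patients.** Suppose the flagged set has ORR 25% and makes up 90% of the IRC-measurable patients. If the left-out 10% have ORR 10%, the full figure is 0.9 × 25 + 0.1 × 10 = 23.5%. If they have ORR 40%, it is 26.5%. Leaving them out can therefore raise or lower the reported ORR.

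**Type I error.** With equal true rates, dilution acts alike in both arms. The exact size of the test at 130 per arm is about 0.0005 for every f above, below the nominal 0.001.

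**Trial-level cost of a missed ORR.** By SAP Figure 1, PFS is tested at 0.040 whatever ORR shows. A negative ORR lowers interim OS alpha from 0.002 to 0.001 and final OS alpha by at most 0.001 (for example 0.050 to 0.049).

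**The case against.** The case for leaving the set alone is reasonable. ORR among randomized patients whom the investigator judged measurable at screening is a coherent, pre-specified quantity. Membership is fixed before randomization, so it cannot depend on arm. An IRC-based set is settled later, because the IRC review is retrospective, and could lose randomized patients whose baseline images are missing or unreadable. The documents also do not describe how the IRC selects lesions: protocol 8.1 refers to an imaging plan for IRC materials and procedures. Disagreement might be rare.

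All of this stands, and it is why replacing the co-primary set is a choice rather than a necessity. It does not answer the narrower point that no planned ORR analysis would show whether the result depends on the mismatch.

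A reader might infer more than the documents support:
- **That patients without an IRC target lesion can never respond.** Table 8 still allows CR.
- **That leaving out unflagged patients also understates ORR.** It mainly costs sample size, and the direction is open.
- **That the test is invalid.** The flag precedes randomization and type I error is preserved.
- **That the missing Non-CR/Non-PD category biases ORR.** SAP 8.1.3 says "the best response as assessed by the IRC using response categories CR, PR, SD, PD and NE will be summarized", which has no place for that outcome. But the table is descriptive, and such a patient is a non-responder under any label.

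**Conclusion.** The point holds as a modest, inexpensive improvement. The mismatch is explicit in both documents and no planned ORR analysis addresses it. Its size is an assumption-based range:

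- With 5-15% of flagged patients lacking an IRC target lesion and 130 per arm, the reported ORR falls by that share in both arms.
- Exact power then falls by about 1 to 3 points at 30% vs 12%, and by about 1 to 2 points at 38% vs 12%.
- If a further 10% of IRC-measurable patients lack the flag, the loss is about 10 points at 30% vs 12% and about 4 to 6 points at 38% vs 12%.
- If the readers agree, there is no loss.

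It would be tempting to conclude that the co-primary analysis is biased in favour of one arm, or that the trial's success turns on this. Neither follows: the effect is not differential by arm, and a missed ORR costs OS at most 0.001 of alpha at each look.

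**What to change.** Before results by arm are seen:

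1. Pre-specify an analysis of IRC-assessed ORR in randomized 3rd line+ patients with at least one target lesion on the blinded IRC baseline read. Run it as a sensitivity analysis beside the current set, or make it the primary ORR set if the sponsor prefers matched readers.
2. State how patients with missing or unreadable baseline images are handled in that set, and report their number by arm.
3. Tabulate investigator-IRC agreement on baseline measurability by arm.

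The cost is SAP wording and a little more analysis work, since the blinded IRC review is already planned. Making the new set primary would also need a protocol amendment under protocol 12.1. The drawback is that membership is known only after the IRC baseline read, which is why the rule in step 2 is needed. Adding a Non-CR/Non-PD row to the IRC best-response table would be tidy but is optional.

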12.3.3 Demographics and Other Baseline Characteristics

Will be summarized in the 3rd line+ population in the same fashion as for the overall, 2nd line + population.

12.3.3.1 Medical History

Will be summarized in the 3rd line + population in the same fashion as for the overall, 2nd line + population.

12.3.3.2 Medical History of Prior Systemic Cancer/Oncology Therapies

Will be summarized in the 3rd line + population in the same fashion as for the overall, 2nd line + population.

12.3.3.3 Previous Radiotherapy and Surgical History

Will be summarized in the 3rd line + population in the same fashion as for the overall, 2nd line + population.

12.3.4 Patient disposition

Will be summarized in the 3rd line + population in the same fashion as for the overall, 2nd line + population.

12.3.5 Protocol Deviations

Will be handled in the 3rd line + population in the same fashion as for the overall, 2nd line + population.

Protocol No.: POL6326-009

Version 3.0

12.3.6 Treatments and Medication

12.3.6.1 Prior and Concomitant Medication

Will be summarized in the 3rd line + population in the same fashion as for the overall, 2nd line + population.

12.3.6.2 Subsequent Anti-cancer Therapy

Will be summarized in the 3rd line + population in the same fashion as for the overall, 2nd line + population.

12.3.6.3 Exposure/Study Medication

Will be summarized in the 3rd line + population in the same fashion as for the overall, 2nd line + population.

12.3.7 Efficacy Analyses

12.3.7.1 Co-Primary Endpoints: Objective Response Rate and Progression Free Survival

Objective Response Rate

Will be analyzed in the 3rd line + population in the same fashion as for the overall, 2nd line + population. The alpha allocation will be 0.001 2-sided.

Progression Free Survival

Will be analyzed in the 3rd line+ population in the same fashion as for the overall, 2nd line + population. The alpha allocation will be 0.040 2-sided. If PFS in the 3rd line + population is met at the allocated alpha level, PFS in the overall population will also be formally tested at the same alpha level.

